#### **Patient Recruitment**

A diagnostic knee MRI (through CHCO or an outside facility) will have been performed as standard of care prior to study participation, utilizing dGEMRIC, a Non-contrast MRI or a MRI with and without contrast in patients with a high clinical suspicion for osteochondritis dissecans. The study is posted on the clinicaltrials.gov website and patients and/or their parents may call and inquire about eligibility.

Lesions will be classified according to Di Paola et al classification [33]

This uses 5 stages as follows:

Grade 1: Small change of signal without clear margins of fragment,

Grade 2: osteochondral fragment with clear margins but without fluid between fragment and underlying bone,

Grade 3: fluid is visible partially between fragment and underlying bone,

Grade 4: fluid is completely surrounding the fragment, but the fragment is still in situ;

Grade 5: fragment is completely detached and displaced.

Only patients with Di Paola stage 1 or 2 lesions will be approached for study participation and consented into the study.

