### **Inclusion Criteria**

1. Male or female age 10 - 17 inclusive with open physis confirmed by MRI
2. Documented symptomatic stable juvenile osteochondritis dissecans of the knee based on MRI without changes of osteoarthritis and no prior history of knee surgery. The MRI diagnosis must be within a 3 month time period prior to consent.
3. The patient must be able to hold still without sedation for approximately 1 hour and must pass MRI screening evaluation for retained metal.
4. Patients with Di Paola stage 1 or 2 lesions

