### **Randomization**

After consent, the study personnel will open a sealed envelope containing the randomization assignment. The envelopes will also contain the appropriate patient handouts and instructions. Randomization will be balanced within the study to allow equal assignment to each treatment group. The randomization envelopes will be prepared by [name], the study biostatistician or her designated staff, using a random balanced allocation randomization protocol.

A study ID participant list in REDCap will be filled out by [name]/[name], their research staff or the Radiology Research Associate, [name], and will record the treatment assignment. The study personnel will e-mail the study statistician with the patient's study id number and the treatment assignment, recorded as 1 or 2. The study personnel will keep a key file containing the patients' names and study id numbers.

The study will not be blinded to the patient, to the patient's parent, or the physician administering the PRP injections. However, the study imaging and results will be kept blinded to the PI, [name], Pediatric Radiologist and the study biostatistician until the blind is broken, shortly before manuscript submission. Thus, treatment assignment will simply be recorded as 1 or 2 for the datasets.

The informed consent will make it clear to the patient and the patient's parents that the child will be randomized to one of two treatments: platelet-rich plasma injection with standard of care, or standard of care alone. Some patients may not like their assignment. If the patient wishes to, the patient who does not like their assignment can at that point drop out of the study and proceed with whatever care they choose. Such randomization related dropouts will be recorded.

This participant list in REDCap will contain the following information: At a minimum, empty columns are provided to record the following:

- Subject name
- Medical record number
- Patient and parent email addresses
- Initials of person enrolling the subject
- Date of enrollment.
- Treatment assignment
- List of required surveys to indicate completion

Other empty columns can be added on request.

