### **Proposed statistical analysis for Aim 1: Cartilage healing**

The T1GD value on dGEMRIC measures GAG content in cartilage. Higher T1GD values are associated with higher GAG content in the tissue, a positive measure of cartilage health. We assume that the value is approximately normal.

We plan to fit a general linear mixed model [39] for the outcome of T1GD. Predictors will include the visit at which the T1GD test was performed (initial MRI and 6 months), whether the site was weight bearing or not, and whether the side was affected or not, and the treatment group. Age will be included as a covariate. An unstructured covariance will be used to account for correlation between T1GD measurements on the same participant. Jackknifed-studentized residuals will be examined to assess normality, and transformations will be applied as appropriate.

We will test the null hypothesis of no time by treatment by weight bearing surface by affected side interaction. Given a non-significant interaction, we will test the main effects of time and treatment, comparing the difference between the weight-bearing and non-weight bearing surface for the affected and non-affected sides. Estimates, 95% confidence intervals, and p-values will be produced. All hypothesis tests will be performed using the Wald test with Kenward and Roger degrees of freedom[40] . Hypothesis tests will be performed at the Bonferroni corrected alpha of  $0.05/3 = 0.017$ .

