### **Proposed statistical analysis for Aim 2: Functional Recovery and Symptoms**

We will analyze scores for each subscale of the KOOS-child, and the overall score produced by the pedi-IKDC range from 0 to 100, with higher scores indicating improved knee function. Each measure is approximately normal.

We describe the analysis for Aim 2, Sub-aim 2.1. The analyses for the other sub-aims are exactly parallel.

We plan to fit a general linear mixed model [39] with the pain subscale of the KOOS-child as the outcome. Predictors will include the visit at which the survey was given (6 weeks, 12 weeks, 6 months, 9 months and 12 months) and treatment group. Age will be included as a covariate. An unstructured covariance will be used to account for correlation between measurements on a single participant. If the resulting model fails to converge, a spatial exponential covariance will be used. Jackknifed-studentized residuals will be examined to assess normality, and transformations will be applied as appropriate.

We will test the null hypothesis of no polynomial time trend by treatment interaction. If the time-by-treatment test is non-significant, we will step down to test the main effects of time and treatment. Estimates, 95% confidence intervals, and p-values will be produced.

All hypothesis tests will be performed using the Wald test with Kenward and Roger degrees of freedom [40] . Three hypothesis tests may be performed for each outcome, for a total of 12 tests. To control for multiple comparisons, all hypotheses will be tested at the Bonferroni corrected alpha level of  $0.05/12=0.004$ .

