### **Proposed statistical analysis for Aim 3: Correlation of MR Findings and Measures of Functional Recovery and Symptoms**

We plan to fit four general linear univariate models with 6-month T1GD as the outcome. The primary predictor for each model will be the 6 month measurements of the pain subscale of KOOS-child, the ADL subscale of the KOOS-child, the sports subscale of the KOOS-child, and the pedi-IKDC, respectively. In each model, age will be included as a covariate. We will test the null hypothesis of no association between the functional measure and T1GD findings on MR and/or no decrease in DiPaolo score, using an F test. All hypotheses will be tested at the Bonferroni corrected alpha level of  $0.05/4 = 0.0125$ .

Interim analysis and planned interim power analysis.

Because this study has never been done in children, the estimates for power analysis may be incorrect, and the effect of the treatment may be better or worse than that reported in the literature. Thus, after the first six study participants have been recruited, treated, and followed, the investigators will report blinded data to the study statistician, who will perform an interim power analysis using the methods of Gurka et al., 2007 [41].

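### Entry Di Paola stage is known before randomisation but is neither stratified on nor adjusted for; this matters most for the Di Paola change endpoint, where only stage 2 patients can show a decrease

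*Combined protocol and SAP*

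**What the plan says.** **Stage is fixed before allocation.** Patient Recruitment says "Only patients with Di Paola stage 1 or 2 lesions will be approached for study participation and consented into the study", and Inclusion Criteria repeats "Patients with Di Paola stage 1 or 2 lesions". Eligibility is confirmed from the standard-of-care MRI. Randomization then says "After consent, the study personnel will open a sealed envelope containing the randomization assignment".

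**Allocation ignores stage.** "Randomization will be balanced within the study to allow equal assignment to each treatment group". No stratification factor is named.

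**The models ignore stage.**
- Aim 1: "Predictors will include the visit at which the T1GD test was performed (initial MRI and 6 months"), plus weight-bearing site, affected side and treatment. Then "Age will be included as a covariate".
- Aim 2: "Predictors will include the visit at which the survey was given (6 weeks, 12 weeks, 6 months, 9 months and 12 months"), plus treatment group and age. Neither the baseline score nor stage is listed.
- Aim 3: "In each model, age will be included as a covariate".

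**Stage is still the starting point of an outcome.** Specific Aims makes healing on the Di Paola system an alternative to T1GD for Aim 1. The section on the research MRI uses the classification to measure interval change in patients with non-contrast follow-up. Data Analysis Plan scores lesions before and after treatment, and section 9 refers again to interval change. The Aim 1 statistical section specifies no between-arm test of that change.

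**The concern.** The plan's own scale separates the two entry stages: grade 1 is a small signal change without clear margins, and grade 2 is a fragment with clear margins. Grade 1 is also the lowest grade listed. A patient who enters at stage 1 therefore cannot record a lower grade, whatever the treatment does. The share of each arm that can improve is set by its stage mix, and with 12 per arm nothing in the plan controls that mix.

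Two results are exposed. A crude comparison of Di Paola decrease would combine stage mix with healing. The Aim 2 treatment main effect would absorb any stage imbalance to the extent that stage predicts the KOOS-child or pedi-IKDC scores, because neither baseline score nor stage is in those models. If stage were brought in only after an imbalance had been seen, the adjustment would be post hoc.

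**Working it through.** **Inputs from the documents.** 24 patients, 12 per arm (Description of Population); entry stages 1 and 2, lowest grade 1 (Patient Recruitment); T1GD SD 50 ms, difference 85 ms, power 0.93 (Power Analysis); alpha 0.05/3 = 0.017 for Aim 1 and 0.05/12 = 0.004 for Aim 2.

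**Assumptions, because the documents give no figure.** The stage mix, the share of stage 2 lesions that improve, the split between dGEMRIC and non-contrast MRI, and the association of stage with outcome.

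**1. How often the arms differ.** With K stage 2 patients among 24, the number x in one arm is hypergeometric and the arms differ by |2x − K|.

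| K | P(differ by 2 or more) | P(differ by 4 or more) |
|---|---|---|
| 8 | 0.667 | 0.193 |
| 12 | 0.684 | 0.220 |
| 16 | 0.667 | 0.193 |

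**2. Effect on Di Paola decrease.** If a share p of stage 2 lesions improves in both arms, the crude arm difference is p × (difference in stage 2 count)/12. With 8 v 4 and p = 0.5, that is 4/12 = 33% v 2/12 = 17%. Within stage 2 the same data give 4/8 v 2/4, 50% in each arm. The 33% v 17% gap comes wholly from stage mix.

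If only a non-contrast subset contributes, take as an alternative scenario 12 patients split 6:6 with 6 at stage 2. The chance of a difference of 2 or more is 1 − C(6,3)²/C(12,6) = 1 − 400/924 = 0.567. Two patients in six is again a 33-point gap in the share able to move down.

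**3. Effect on the Aim 2 treatment main effect.** A 4-patient imbalance shifts the arm difference by (4/12) × g, where g is the stage difference in SD units. For g = 0.5 and 1.0 the shift is 0.17 and 0.33 SD. The standard error of a single-visit difference is √(2/12) = 0.41 SD. At g = 0 the shift is zero.

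**4. Effect on the time-by-treatment tests.** I forced an 8 v 4 imbalance with a time-constant stage effect and fitted by generalised least squares with an unstructured covariance and complete data, for 2 and for 5 visits. Adding a stage main effect left every time-by-treatment estimate and standard error unchanged (2 visits: estimate 1.024 in absolute value, SE 1.042, both ways). Only the treatment main-effect term moved.

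**5. Price and possible gain of the covariate.** The plan's 0.93 is matched by a two-sided 6-month comparison at 0.017 (noncentral t, 22 df: 0.933). At two-sided 0.05 the same comparison gives 0.978. The plan does not state sidedness or the exact contrast; that is a separate matter. Adding stage uses 21 df and a variance inflation of 1 + 1/22. With half the patients at stage 2, R² = 0.25g²/(1 + 0.25g²).

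| Stage difference g | R² | Power for 85 ms at 0.017 |
|---|---|---|
| unadjusted | – | 0.933 |
| 0 (not prognostic) | 0 | 0.920 |
| 0.5 SD | 0.059 | 0.936 |
| 0.75 SD | 0.123 | 0.951 |
| 1.0 SD | 0.20 | 0.968 |

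For a smaller assumed effect of 60 ms, power falls from 0.641 to 0.615 if stage is not prognostic. At the Aim 2 alpha of 0.05/12, the same formula with effects of 60/50 = 1.2 and 85/50 = 1.7 SD gives 0.422 to 0.394 and 0.817 to 0.790. The loss is 1 to 3 points throughout.

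**The case against.** The strongest reply has four parts.

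- **Randomisation already covers chance imbalance.** This is correct. Imbalance is random error and the nominal error rate allows for it. A reader might infer that the trial is biased; it is not. Conditioning on stage improves how one realised comparison is read, and its precision if stage is prognostic.
- **The lead tests do not need stage.** Aims 1 and 2 both begin with an interaction involving time, and the Aim 1 outcome visits include the initial MRI. A reader might infer that an imbalance flows into T1GD and every score analysis. Step 4 shows that it does not, unless the stage effect varies over time; a stage main effect would not address that either.
- **No prognostic link is documented.** This also stands for T1GD and the scores, so any precision gain is conditional. It does not answer the Di Paola point, which follows from the lowest listed grade. That point would soften only if resolved grade 1 lesions were given a lower score, and none is listed.
- **Other gaps come first.** The plan specifies no between-arm test of Di Paola change, and the baseline KOOS-child and pedi-IKDC scores are collected but absent from the Aim 2 predictors. Both are fair. The first is a reason to write the test with stage built in; the second is a more direct loss of precision than stage.

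A reader might also infer that stage is used nowhere. The documents do not support that: it is the starting value of Di Paola change, and Aim 3 names a decrease in that score.

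**Conclusion.** The point holds in a limited form. Entry stage is known for all patients before randomisation and is neither stratified on nor adjusted for.

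- **Di Paola change: the main consequence.** Only stage 2 patients can show a decrease. An imbalance of 4 or more patients has a probability of about one in five if 8 to 16 of 24 are stage 2. At 8 v 4 with 50% improving, it produces a 17-point gap with no treatment effect. The floor is a property of the listed scale; the stage mix and the 50% are assumptions.
- **Aim 2 treatment main effect: secondary.** The shift is 0.17 to 0.33 SD for a 4-patient imbalance if stages differ by 0.5 to 1.0 SD, and nil if stage is not prognostic. Even the upper figure is below the 0.41 SD standard error.
- **Time-by-treatment tests in Aims 1 and 2: not affected** by a stage effect that is constant over time.

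The documents support no claim of a definite power gain for T1GD.

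**What to change.** 1. Specify the between-arm comparison of Di Paola change as an exact test stratified by entry stage. Report the share with a decrease among stage 2 patients separately.
2. Prespecify entry stage (1 v 2, as read before randomisation) as a covariate beside age in the four Aim 2 models, stating that it serves the step-down treatment main effect.
3. Tabulate entry stage by arm at baseline.
4. In the Aim 1 T1GD model, treat a stage main effect as optional, because the initial MRI is already among the outcome visits.

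This is a change of analysis wording and needs no new data. It costs one degree of freedom per model, about 1 to 3 points of power if stage is not prognostic. Any gain in precision depends on a stage-outcome association that the documents do not give.

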#### **Pre-Screening Visit**

Study subjects will be recruited from current patient population at Children's Hospital Colorado or first time patients of [name]/ [name] or their colleagues at the Children's Hospital Sports Medicine Clinic. They will be identified and recruited during routine office visits. Study subjects may also come directly to the PI/Research Associate through the clinicaltrials.gov website. The initial MRI scan, initial x-rays, and any follow-up x-rays will be performed as standard of care and will follow hospital policy, and they will be used to assess and confirm eligibility. Female patients included in the study, over the age of 12 who have begun menstruation will undergo a urine pregnancy test prior to the research MRI obtained at 6 months.

#### **Inclusion & Exclusion Criteria**

Patients will be recruited based on the following eligibility criteria:

### **Inclusion Criteria**

1. Male or female age 10 - 17 inclusive with open physis confirmed by MRI
2. Documented symptomatic stable juvenile osteochondritis dissecans of the knee based on MRI without changes of osteoarthritis and no prior history of knee surgery. The MRI diagnosis must be within a 3 month time period prior to consent.
3. The patient must be able to hold still without sedation for approximately 1 hour and must pass MRI screening evaluation for retained metal.
4. Patients with Di Paola stage 1 or 2 lesions

### **Exclusion criteria**

1. Patients with polyarticular disease (not applicable to polyarticular disease of the knees as the most symptomatic knee will qualify for the study)
2. Patients with blood disorders (Blood disorders (thrombopathy, thrombocytopenia, anemia with hemoglobin <9g/dL).
3. Patients who had intra-articular treatment with steroids within 3 months
4. Patients who are pregnant or nursing at the time of consent.
5. Patients with inflammatory arthritic conditions (e.g. rheumatoid arthritis)
6. Non-English speaking patients. (Scores used for evaluation have not been validated in Spanish)
7. Patients who had previous knee surgery
8. Additional disabilities in any of the lower limbs that would interfere with any of the clinical assessments.
9. Chronic use of NSAID (defined as taking NSAID regularly every week for the last 6 months), steroids or chemotherapy drugs
10. Treatment with NSAIDs within 15 days prior to randomization in this study
11. Patients with a BMI over 30. Due to the fact that this study utilizes an injection technique which may be inaccurate in obese subjects.
12. Patients with a contraindication to MRI including: patients with cardiac pacemaker or non-approved intracranial vascular clip, and those with orthopedic hardware as the resulting artifact can complicate interpretation
13. Patients with acute or chronic renal failure
14. Patients with a previous anaphylactic reaction to gadolinium enhanced MRI.
15. Patients with Di Paola stage 3 or 4 lesions
16. Patients who received a MRI diagnosis of OCD but do not have the specific cartilage imaging sequences.
17. Clinical or laboratory evidence of septicemia

### **Consent/Assent**

Informed consent/assent will be obtained by the PI/ Pediatric Radiologist, [name], or his research staff, Sports Medicine physicians, [name]/[name] or their research staff.

Consent will be obtained in the Interventional Radiology suite, Radiology Fluoroscopy suite, physician office or other private room. A signed and dated copy of the consent/assent will be given to the subject. Patients will be required to sign an assent form. The parent or legal guardian will be required to sign a consent form. Subject comprehension will be assessed by asking the subject/subject family if they understand and are willing to participate. Patients will have the option to take the consent document home and review it before consenting to participate in the study. Patients will have the option to combine the consent visit (visit 0) with the baseline visit (visit 1).

### **Randomization**

After consent, the study personnel will open a sealed envelope containing the randomization assignment. The envelopes will also contain the appropriate patient handouts and instructions. Randomization will be balanced within the study to allow equal assignment to each treatment group. The randomization envelopes will be prepared by [name], the study biostatistician or her designated staff, using a random balanced allocation randomization protocol.

A study ID participant list in REDCap will be filled out by [name]/[name], their research staff or the Radiology Research Associate, [name], and will record the treatment assignment. The study personnel will e-mail the study statistician with the patient's study id number and the treatment assignment, recorded as 1 or 2. The study personnel will keep a key file containing the patients' names and study id numbers.

The study will not be blinded to the patient, to the patient's parent, or the physician administering the PRP injections. However, the study imaging and results will be kept blinded to the PI, [name], Pediatric Radiologist and the study biostatistician until the blind is broken, shortly before manuscript submission. Thus, treatment assignment will simply be recorded as 1 or 2 for the datasets.

The informed consent will make it clear to the patient and the patient's parents that the child will be randomized to one of two treatments: platelet-rich plasma injection with standard of care, or standard of care alone. Some patients may not like their assignment. If the patient wishes to, the patient who does not like their assignment can at that point drop out of the study and proceed with whatever care they choose. Such randomization related dropouts will be recorded.

This participant list in REDCap will contain the following information: At a minimum, empty columns are provided to record the following:

- Subject name
- Medical record number
- Patient and parent email addresses
- Initials of person enrolling the subject
- Date of enrollment.
- Treatment assignment
- List of required surveys to indicate completion

Other empty columns can be added on request.

. When a subject is enrolled in the study, s/he is assigned a confidential study identifier by adding his/her name in chronological order, to the very next empty row available on the REDCap participant list. The subject maintains this study ID for the remainder of the trial and, thereafter, the Study ID is used on all research files, randomization Lists, and other research documents.

A research assistant, [name]/[name], or [name] will fill out the assignment log and randomized assignment list.

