## **Informational patient brochure/Compliance Surveys/ Baseline and Follow-up KOOS and IKDC surveys/Clinical Assessments**

An informational brochure (see attached) will be used to assist in the recruitment of eligible patients. The brochure will describe the autologous platelet rich plasma treatment, process, risks, appointment information and post procedure information.

Patients randomized to the PRP Treatment arm will receive a Pre and Post-Injection Instruction handout (see attached). The handout describes how the patient should prepare for the PRP injections and what to expect after the injection.

The study personnel who consents the patient will request the patient's and parent's email addresses which will be used to send out the weekly and monthly surveys.

For the first 6 weeks of the study, all patients will receive a weekly Compliance Survey (see attached) created by the Sports Medicine physicians to validate compliance with 1. non-weight bearing, 2. wearing a brace, 3. at home PT exercises, and 4. no high impact activity.

**KOOS/IKDC surveys:** All patients will receive a baseline survey and repeat surveys at 6 wks, 12 wks, 6 m, 9m, and 12 months, which is considered standard of care, on the CHCO main campus or one of the following satellite locations (South, Parker, Centennial, Uptown/St Joseph's or Broomfield). The surveys will include the following outcome scales: Pedi IKDC and KOOS-child.

The Pedi-IKDC is a modified version of the widely used International Knee Documentation Committee (IKDC) Subjective Knee Form, which is a knee specific measure of symptoms, function and sports activity. The Pedi-IKDC was developed for use with children and adolescents ages 10-17. The reliability and validity of the Pedi-IKDC has been demonstrated to be acceptable in young patients with a variety of knee disorders.

Similarly, the KOOS – child is a pediatric version of the Knee Injury and Osteoarthritis Outcome Score (KOOS). The KOOS-child score is subdivided and scored in five categories: Pain, Other Disease-Specific Symptoms, Activities of Daily Living Function (ADL), Sport and Recreation Function and Knee-related Quality of Life (QOL).

[http://www.actaorthop.org/sup\\_files/5292.pdf](http://www.actaorthop.org/sup_files/5292.pdf)

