[http://www.sportsmed.org/uploadedFiles/Content/Medical\\_Professionals/Research/Grants/IKDC\\_Forms/Pedi-IKDC%20Form.pdf](http://www.sportsmed.org/uploadedFiles/Content/Medical_Professionals/Research/Grants/IKDC_Forms/Pedi-IKDC%20Form.pdf)

Clinical follow up will also be performed following injections or the commencement of conservative therapy at 6 weeks, 12 weeks, 6 months, 9 months, and 12 months by [name]/[name] or their colleagues on the CHCO main campus or one of the following satellite locations (South, Parker, Centennial, Uptown/St Joseph's or Broomfield). The clinical findings documented will include presence or absence of a joint effusion, overall range of motion, presence or absence of joint line tenderness and positive or negative Wilson's test 6 week follow up for both groups will also include radiographic evaluation, which is standard of care. If

the patient is clinically or radiographically improving, physical therapy will be started as standard of care, following the same treatment protocol initially with closed kinetic chain, non-impact exercises. Patients will then slowly return to impact activities as tolerated over 3 to 4 months.

A patient Timeline of Activity has been created for each arm of the study (see two attachments). The Timeline describes the weekly and monthly events that will occur during this study and can be handed to the patient following the consent and randomization process.

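### Free improvement: the sealed randomisation envelopes also hold handouts that appear to differ by arm, with no safeguard described, so unopened envelopes may be distinguishable

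*Combined protocol and SAP*

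**What the plan says.** The Randomization section of the combined protocol and SAP sets the procedure: "After consent, the study personnel will open a sealed envelope containing the randomization assignment". It then adds a packing rule: "The envelopes will also contain the appropriate patient handouts and instructions". The study biostatistician or designated staff prepare the envelopes, "using a random balanced allocation randomization protocol".

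The section on the brochure, surveys and clinical assessments describes two kinds of patient paper tied to the arm:

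- "Patients randomized to the PRP Treatment arm will receive a Pre and Post-Injection Instruction handout". No counterpart is described for the conservative arm.
- "A patient Timeline of Activity has been created for each arm of the study". This timeline "can be handed to the patient following the consent and randomization process"; the text does not say whether it travels in the envelope or separately.

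The form under Subject ID Assignment Log records the date, time and signature when an envelope is opened. The Randomization section states that patients, parents and the physician giving the injections are not blinded.

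**The concern.** A sealed envelope conceals an assignment only if envelopes for the two arms look and feel alike until they are opened. If one arm's envelope carries different papers, the seal still prevents reading the assignment but does not prevent guessing it from thickness or weight.

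This matters because the envelope is opened after consent. Someone who could guess the next arm beforehand could, knowingly or not, let that guess affect who is enrolled next. In an open-label trial, concealment up to the moment of assignment is the main protection against such selection. Keeping the imaging reader and the statistician unaware of treatment protects assessment and analysis; it does not protect the make-up of the arms. With 12 patients per arm, there is little room for chance to dilute even a few selected enrolments.

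**Working it through.** The plan states no figure on this point and no formula applies. The check is to read the relevant sections together.

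1. **Do the envelopes hold more than the assignment?** Yes. The Randomization section says so directly.
2. **Do the extra contents depend on the arm?** Probably. The section calls the handouts *appropriate*, a word with little purpose if every patient received the same set. Of the papers described for use after assignment, one is for PRP patients only and the other exists in two versions, one per arm.
3. **What would each envelope contain if the papers described were packed as the Randomization section directs?**
   - PRP: assignment, PRP timeline, injection-instruction handout.
   - Conservative: assignment, conservative timeline.

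   On that reading the PRP envelope holds one item more. This is an inference: the document lists the contents for neither arm, and the papers themselves are attachments that are not reproduced.
4. **Is there a safeguard that would make unopened envelopes alike?** None is described. The sections on consent, randomisation, the assignment logs and patient papers mention no opacity, matched weight or thickness, filler sheets, or separate supply of all arm-specific papers.
5. **Do the stated controls close the gap?** Not fully. Preparation by the biostatistician's group, sealing, and opening after consent limit who knows the list and stop the assignment being read early. The opening record documents when an envelope was opened and by whom. None of these makes two unopened envelopes feel the same.
6. **Can the size be calculated?** No. That would require the physical difference between envelopes, who handles them before consent, how often a guess was right and acted on, and how prognosis differed among the patients affected. The document gives none of these.

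**The case against.** The strongest reply is that the step from different papers to distinguishable envelopes is not documented. The injection handout is something PRP patients will receive, with no statement that it comes in the envelope. The timeline wording fits separate handover equally well. Conservative patients might be given written brace, activity or home-exercise instructions, which could make their packet as thick or thicker. Whether one sheet could be felt is unknown. All of this stands, and it is why the point says *may be distinguishable*. It does not remove the point: the only statement about where handouts are kept puts them in the envelope, and concealment should not depend on the packets happening to match.

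A reader might go further in three ways that the document does not support:

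- **That the person taking consent holds the next envelope and can feel its contents.** Custody before consent is not stated. Consent/Assent lists several people who may obtain consent, and Randomization says only that study personnel open the envelope.
- **That recruiters control the timing of enrolment.** Consent/Assent, and the section on schedules following randomisation, give the option of deferring to the patient. Some influence by recruiters is possible, but these sections do not establish it.
- **That a bias in milliseconds can be attached.** Suppose two better-prognosis patients were steered to PRP and two worse-prognosis patients to control, each one SD (50 ms in Power Analysis) from the mean at follow-up. The shift would be 2/12 × 50 + 2/12 × 50 = 16.7 ms, or 20% of the 85 ms planning effect. If the steering were instead on a one-SD difference in baseline T1GD, the planning correlation of 0.2 would carry over only 0.2 × 16.7 = 3.3 ms, or 4%, before any adjustment. The number steered is invented in both cases, so neither figure estimates anything about this trial. Nor is there a basis for saying that all 24 assignments are exposed.

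**Conclusion.** The point holds as a free improvement. The protocol directs that handouts be placed in the sealed envelopes, describes patient papers that differ by arm, and describes nothing that would make unopened envelopes alike. Allocation concealment may therefore be weaker than the sealed-envelope procedure suggests, in a 24-patient trial where patients, parents and the injecting physician are not blinded.

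This rests on two readings: that *appropriate* means appropriate to the arm, and that at least some of the arm-specific papers are the ones packed. It does not show that PRP envelopes are thicker, that anyone has guessed an assignment, or that selection has occurred. The size of any bias cannot be calculated from the document. No stated sample size, power or alpha is affected.

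**What to change.** Amend the packing sentence in the Randomization section so that each opaque, sequentially numbered, sealed envelope contains only an assignment card, identical in format for both arms. Keep the arm-specific handouts, instructions and timelines in separate stock, to be given once the envelope has been opened and the opening logged. The existing form for date, time and signature can serve as that record, and the timeline wording already allows handover after randomisation.

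The cost is one protocol sentence and repacking of the unused envelopes. The same papers still reach the same patients, and the analysis is unchanged.
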